Although the Anemia Mukt Bharat national guidelines^{2,3} indicate that IV iron sucrose or ferric carboxymaltose (FCM) may be considered as a first-level treatment when anemia has been detected late in pregnancy or when compliance to an oral iron regimen is likely to be low, the RAPIDIRON Trial will use ferric carboxymaltose in addition to iron isomaltoside (also known as. ferric derisomaltose). However, IV iron sucrose will not be used for study-related infusions, primarily because clinical trials have not shown that it has advantages over single-dose IV iron. 24,25 Further, the package insert for iron sucrose indicates the need for five individual and staggered infusions, which results in greater potential for non-compliance of iron sucrose compared to newer single-dose IV iron formulations. A 2018 article in the Journal of the Indian Society of Hematology and Blood Transfusions states that the problem of multiple infusions "has been circumvented by the newer preparations like iron isomaltoside and ferric carboxymaltose which allow larger infusion doses."26 Faculty of the All India Institute of Medical Sciences recently completed a study that provided evidence that more convenient single-dosing of IV iron resulted in a significantly higher rise in Hb over 12 weeks compared to iron sucrose. Those receiving IV iron also had greater improvement in fatigue scores and required fewer facility visits for treatment. No serious adverse events occurred in either study group.²⁴

Two weeks following an IV iron treatment, only IV iron participants will visit the PHC or CHC (Visit #4 in Appendix B). A blood sample will be collected and analyzed to determine serum phosphate levels. Recent published reports have associated intravenous ferric carboxymaltose with a significant reduction in serum phosphate level in some patients ²⁷ although the clinical significance is unclear.

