Assuming the study is not stopped for efficacy, one formal interim analysis for futility will be completed based on a data snapshot taken when the anemia outcome is available for 666 subjects per group (1/2 of expected information). The interim analysis for futility will involve the conditional power associated with two hypothesis tests: the two-degree of freedom CMH test of differences in prevalence of anemia prior to delivery across the three treatment arms and the two-degree of freedom test of differences in risk of LBW across the three treatment arms. If analyses for both primary efficacy outcomes show a conditional power of less than 0.2 based on the observed data at the time of the interim analysis and the assumed effect for the study design, the Data and Safety Monitoring Board (DSMB) may consider recommending that the study be stopped.

The analysis for safety will have two components. First, point and 97.5% confidence interval estimates of the risk of mortality and incidence of at least one SAE will be developed for each of the three treatment arms. If the interval estimates provide evidence that either of the active IV iron treatment arms has significantly higher risk of either mortality or adjudicated SAE incidence than the active comparator arm (oral iron), the DSMB will consider recommending stopping enrollment on that active IV iron treatment arm. In making the recommendation, the DSMB can consider the overall risk profile of the treatment arms and any evidence of efficacy that has been accumulated at the time of the interim analysis.

Additional details of the planned interim analysis will be developed in collaboration with the DSMB and the details will be included in a formal Interim Analysis Plan that will be approved by the DSMB prior to enrollment.

5. Safety Analyses

All safety analyses will be descriptive based on the safety cohort with no planned formal inference for safety. All adverse events will be summarized by system organ class by arm with point and interval estimates of the risk of each of these events estimated by either exact binomial methods or normal approximations to the binomial as appropriate for the incidence of the event. Descriptive statistics will also be generated for maternal and infant mortality and for incidence of SAEs.

6. Analysis Cohorts

- A. Intent-to-treat (ITT) cohort: All randomized study participants will be included using group assignments as randomized.

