- B. Per-protocol cohort: All study participants who receive the complete, recommended dosage of the randomly assigned IV iron formulation between the beginning of the 14th week and 17 weeks 0 days of pregnancy will be included in this cohort as will all study participants assigned to oral iron therapy who take equal to or greater than 75% of prescribed pills (as each woman given oral iron will be asked to maintain a diary indicating her pattern of use). However, use of any non-study-provided iron preparation post-randomization will represent an exclusion for the purpose of the per protocol analysis. Additionally, a participant assigned to an IV iron arm that receives only a portion of the recommended dosage for the randomly-assigned IV iron formulation will also be excluded.
- C. Safety cohort: All study participants who are randomized and receive either the provided oral iron tablets or at least some portion of the one-time, recommended dosage of the assigned IV iron formulation and who provide any safety data subsequent to treatment will be included in this cohort. For all safety analyses, these participants will be included in the analysis based on treatment actually received, not by randomization arm.

Assignment of patients into the various cohorts and treatment arms will be determined based on a masked data review prior to initiation of analyses.

F. Gender/Minority/Pediatric Inclusion for Research

Since this study is designed to assess benefits of single-dose IV iron administration to pregnant women with iron deficiency anemia, such women will necessarily constitute the participants to be randomized for this trial.

The study is to be carried out in two states of India; thus, participants will be classified as adult female Asians. Pregnant women utilizing facilities classified in the Indian public health system as primary or community health centers will have the opportunity to participate if they meet specified eligibility criteria. No pregnant woman will be excluded because of socio-economic status or other

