Side effects typically listed for oral iron include the following: nausea or upset stomach, diarrhea, faintness, vomiting, constipation and black stools. These side effects may not be considered serious if occurring only periodically, but many studies indicate that some of these side effects are quite common and can affect up to 70% of those prescribed the oral iron formulation most often recommended in India (ferrous sulfate). Side effects are often cited as the reason for a high percentage of those prescribed oral iron failing to adhere to instructions for taking the recommended tablets or not taking them for the recommended period of time. Thus, perhaps one of the most serious problems with oral iron is that it's not taken as prescribed. Additionally, a large portion of those that take oral iron per instructions experience side effects and simply cannot tolerate taking the drug; consequently, such symptoms may cause dietary changes that result in less than ideal weight gain during pregnancy.

5. Description of Procedures for Protecting Against or Minimizing Potential Risks

[name] has authored several articles comparing IV iron formulations. In one of these articles, he commented that newer formulations with carbohydrate shells which bind elemental iron more tightly and allow slower release are much safer than older formulations; consequently, serious adverse events are marginal to absent in prospective trials. Minor reactions (such as mild arthralgia/myalgia of the chest or flank or facial flushing) abate without the need for therapy.³⁶ In a 2017 article, he stated that evidence indicates that single-dose formulations currently available in the US are "all safe and effective and there are no major, clinically important differences."³⁷ The literature on both ferric carboxymaltose and iron isomaltoside supports this claim. The preponderance of recent reviews on the use of IV iron indicate that serious adverse events are rare, and that infusion reactions are not common when the newer single-dose formulations are used. However, the very low risk of severe infusion reaction should not be ignored. A remedy for minimizing risk has been proposed by Gomez-Ramirez, Shander, Spanh, [name] and others: "As preventive measures, prior to the infusion, staff should inform all patients about infusion reactions and identify those patients with increased risk of hypersensitivity

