The DSMB met remotely to provide input into this protocol; and they are scheduled to meet again to approve the DSMB charter and ensure adequacy of the informed consent form. The DSMB will review the Data and Safety Monitoring Plan and give specific instruction if it determines the list of items to be reported and forwarded for review should be expanded. The DSMB will meet again approximately 3 months after initiation of recruitment. Thereafter, the DSMB will meet approximately every 6 months until all study participants have completed all study visits and data have been collected for outcomes through 42 days post-delivery. The DSMB may revise the meeting schedule if workload justifies this. If a scheduled meeting is considered too remote to review an SAE and determine relevant action, information may be distributed to DSMB members via email and input sent to the DSMB Chair who can communicate a recommendation representing consensus among DSMB members to senior key personnel of the study. The Chief Quality and Safety Officer will be the intermediary in supplying appropriate data to the DSMB for review.

2. Description of the Data and Safety Monitoring Plan (DSMP)

For this research, a serious adverse event (SAE) involves a randomized participant that initiated treatment OR the fetus or newborn of such a participant. To qualify as an SAE, at least one criterion below will apply to the event--

- Results in a maternal or neonatal death, or a fetal death greater than 20 weeks gestation;
- Is life-threatening;
- Requires an unanticipated hospitalization or prolongs an existing hospitalization;
- Results in persistent or significant disability or incapacity; and
- Represents other serious or unexpected adverse events that a study investigator feels should be reported, including need for resuscitation.

Study drug reactions will be reported as an SAE if meeting an SAE criterion above; such reactions will be reported as a study-related SAE if they are so confirmed by adjudication. Specified adverse

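### SAEs count only once treatment is initiated, which leaves out never-infused IV women but keeps comparable oral women; early non-serious events are also ascertained unequally between IV and oral arms

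*Combined protocol and SAP*

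**What the plan says.** **Who can have an SAE.** H.2 states that "a serious adverse event (SAE) involves a randomized participant that initiated treatment OR the fetus or newborn of such a participant".

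**Who is analysed.** The safety cohort (E.6.C) is women who received study iron and "who provide any safety data subsequent to treatment will be included in this cohort". They are grouped by the treatment they actually received.

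**How safety is reported.** E.5 says "All safety analyses will be descriptive based on the safety cohort with no planned formal inference for safety", and "All adverse events will be summarized by system organ class by arm with point and interval estimates". No common time window or adjustment for length of observation is given. In E.4, if an IV arm shows significantly higher mortality or adjudicated SAE incidence than oral iron, "the DSMB will consider recommending stopping enrollment on that active IV iron treatment arm". E.4 does not say over which women those risks are computed.

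**When treatment starts.** Under Section D and Appendix B, oral women receive tablets at visit #3. IV women have a separate step, #3a, at which willingness is confirmed again. It may be postponed, but not past 17 weeks 0 days. G.5 lets a randomized woman refuse treatment.

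**When women are seen.** Infused women are watched for at least 30 minutes and an infusion form is completed. Then, "Two weeks following an IV iron treatment, only IV iron participants will visit the PHC or CHC". Appendix B describes that visit (#4) as a phosphate draw and lists no adverse-event enquiry. Visit #5, at 20-24 weeks, is the next for IV women and the first after treatment for oral women. H.2 says that minor side effects of both treatments are collected, without timing or method. E.6.B describes the oral diary as a record of pill use.

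**The concern.** Randomization makes the arms comparable at visit #3. The SAE rule then removes women from the IV arms by a process that barely operates in the oral arm: declining, falling ill or missing the deadline between randomization and infusion. If such women differ in risk from those infused, the IV safety cohort no longer matches the oral one. The SAE and mortality contrast matters because E.4 can lead to a recommendation to stop enrollment on an IV arm.

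For non-serious events the problem is ascertainment. Oral intolerance is part of the trial's rationale; G.4 cites side effects that "can affect up to 70% of those prescribed the oral iron formulation" most often recommended in India. Yet early oral side effects have no scheduled study visit at which to be recorded until #5, whereas infusion reactions are seen as they happen. A crude table by arm sets the two side by side as if they had been looked for equally.

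**Working it through.** **1. Denominator, from the plan's own figures.** Inputs from E.1: low-birth-weight rates 25% and 20%, alpha 0.0245, power 80%, 7.5% missing birth weights. The sidedness of alpha is not stated; two-sided reproduces the figure.

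n = [z(1-α/2)·√(2p̄(1-p̄)) + z(power)·√(p₁(1-p₁)+p₂(1-p₂))]² / (p₁-p₂)²

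With z ≈ 2.249 and 0.842 and p̄ = 0.225, n = 1,332 per arm, as stated. Then 1,332 / (1 - 0.075) = 1,440 per arm, and 3 × 1,440 = 4,320. This gives only the number at risk; the plan states no adverse-event rate by arm.

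**2. Scheduled contact after treatment starts.**

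| | IV arms | Oral arm |
|---|---|---|
| Treatment starts | #3a, by 17w0d | #3, 14w0d to 17w0d |
| First scheduled observation | same day (at least 30 min) | #5 |
| Next | #4, 2 weeks | #6 |
| Scheduled points in all | 7 (#3a, #4, #5-#9) | 5 (#5-#9) |
| Post-treatment phosphate | #4 and #9 | none |

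Oral gap to #5: shortest 20 - 17 = 3 weeks, longest 24 - 14 = 10 weeks.

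**3. SAE restriction.** Let u be the share of an IV arm never infused, with SAE risk r_u, and let r_i be the risk in infused women. The randomized arm's risk is (1-u)·r_i + u·r_u. The safety cohort shows r_i, so it misses the arm's risk by u·(r_u - r_i). At an assumed u = 5%, that is 0.05 percentage points for each point by which the two risks differ.
- If both risks are 20% (assumed), the E.5 table reads 20% versus 20%: no distortion.
- If SAEs restricted to treated women were divided by all randomized women, which E.4 does not rule out, the IV arm would read 0.95 × 20% = 19% against 20%.

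**4. Effect of the safety-data condition.** A woman with no safety data contributes no event, so excluding her shrinks only the denominator. If 0% to 7.5% of 1,440 oral women are excluded (assumed; 7.5% is borrowed from the birth-weight figure), the cohort falls from 1,440 to as few as 1,332. Oral risk is then multiplied by at most 1/(1 - 0.075) = 1.08. The effect is upward.

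**5. Effect of unequal capture.** Assume equal true risk, full capture in the IV arms, a share f of events in the early window, and a share s of those captured in the oral arm. Apparent IV/oral risk ratio = 1/[1 - f(1-s)].
- f = 20%, s = 90%: 1/0.98 = 1.02
- f = 50%, s = 75%: 1/0.875 = 1.14
- f = 80%, s = 50%: 1/0.60 = 1.67

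Steps 4 and 5 act in opposite directions, and f, s and the loss rate are not in the documents.

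**The case against.** Much can be said for the plan. SAEs have one definition and one set of adjudicators in every arm, and are reported within 7 days of notification rather than at visits (H.2, J). Community health workers visit pregnant women in all arms (G.3). Visits #5-#9 are common, and the final safety analysis is descriptive. E.3.B also compares maternal and neonatal deaths, pregnancy losses and stillbirths, and unanticipated or extended hospitalizations by arm, and nothing there restricts these to treated women.

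These points rule out several stronger readings that a reader might infer:
- *Oral women have no contact before 20-24 weeks.* Only a scheduled study visit is missing, though no adverse-event query is described for the health workers' visits.
- *Visit #4 gives IV women an extra round of adverse-event questions.* It is described only as a phosphate draw; extra capture there is plausible but undocumented.
- *The safety-data condition hides oral intolerance.* By itself it raises the oral risk, and a woman known to have stopped because of side effects has supplied safety data.
- *SAEs in untreated IV women are lost altogether.* Many would reappear as secondary outcomes.
- *The planned table would read 19% versus 20%.* E.5 uses the safety cohort, so never-infused women leave both numerator and denominator.

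Two things are not answered. Notification-based reporting does not help a woman whose event is outside the SAE definition. And the descriptive label does not cover E.4, where an IV-versus-oral contrast can prompt a recommendation on enrollment.

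**Conclusion.** The concern holds in two limited forms. First, the rule in H.2 selects women after randomization differently by arm, and the result feeds an interim contrast with no stated denominator. Its size is u·(r_u - r_i) in the safety cohort, and neither factor is given. Secondary outcomes recover part of what is missed.

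Second, IV-versus-oral risks of early non-serious events are ascertained unequally, and post-treatment phosphate cannot be compared with oral iron at all. Under the assumptions shown, unequal capture gives an apparent risk ratio of 1.02 to 1.67 where true risks are equal, while the safety-data condition inflates oral risk by a factor of up to 1.08. The documents determine neither the net size nor its sign.

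It would go too far to conclude that adverse-event risks are not comparable between arms in general. The two IV arms share a schedule and can be compared with each other, and for SAEs and deaths the ascertainment problem is weaker because reporting does not depend on visits.

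**What to change.** 1. **H.2:** collect SAEs from randomization in all randomized women and their fetuses or newborns.
2. **E.4 and E.5:** add SAE and mortality tables by randomized arm with all randomized women as denominator, beside the as-treated safety-cohort tables.
3. **E.5:** keep the overall adverse-event table and add one that separates (i) infusion-day, visit #4 and phosphate findings, IV arms only, from (ii) events reported at the visits common to all arms, #5-#9. Note beneath it that early oral side effects are recalled at #5 and that part (ii) leaves out infusion reactions. Part (ii) must not replace the overall table, since alone it would favour IV iron.
4. **E.6.C:** report how many women in each arm the safety-data condition excludes, and show risks over all treated women as a sensitivity analysis. It should not become the main analysis, because it counts women with no data as event-free.

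The cost is a few more SAE forms from untreated women and one extra table set. Sample size, visits and treatment do not change.

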Except for blood samples obtained from pregnant women and analyzed onsite at the initial screening visit to determine Hb level, blood collected subsequently for study-related purposes will be sent to the central laboratory designated for each of the four research sites. Use of the specified central laboratories will ensure greater standardization of laboratory procedures, access to appropriate and dependable laboratory equipment, compliance with laboratory quality control measures, and confidence in test results. The central laboratories of the four participating study hospitals will ensure availability of results for entry into the *RAPIDIRON* database. Medical Officers (or designated clinical staff) of PHCs or CHCs will be provided test results when needed. Hemoglobin values will be sent throughout the course of the study. TSAT and ferritin indices will be forwarded to PHCs and CHCs to enable eligibility screening for randomization at the third visit. Glucose levels will be provided subsequent to screening for gestational diabetes; and out-of-range serum phosphate results for blood collected twice post-treatment from women in the IV arms will be provided for review by PHC or CHC clinical staff.

All pregnant women completing visit #2 will return to the PHC to complete eligibility screening for randomization. When a woman's dating ultrasound indicates a singleton pregnancy of less than 14 weeks, unless medically indicated, she will not be scheduled to go to the PHC or CHC until she reaches the 14th week of pregnancy. Visit #3 is intentionally designed to occur between the interval of 14-17 weeks of pregnancy to coincide with antenatal care recommendations of the Ministry of Health and Family Welfare. Further, the visit is timed to ensure that anemia treatment for randomized participants will be initiated early in the second trimester, up to 17 weeks 0 days, as there is no safety data relative to use of IV iron in the first trimester.

During visit #3, the inclusion and exclusion criteria (found on page 17) will be applied to determine if a pregnant woman is eligible for continued study participation and randomization. Data from the Maternal Newborn Health Registry, funded by NICHD in association with its Global Network for Women's and Children's Health Research, were used to assess the impact of various levels of

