events, other unexpected adverse drug reactions (not qualifying as an SAE by adjudication), and minor side effects reported by study participants will be reported to and monitored by the DSMB. Specific instructions will be provided for reporting an infusion reaction so that it can be determined how quickly the reaction resolved and what was done to facilitate resolution. Minor side effects of oral iron or IV iron will be collected during the study. If data indicate that any of the side effects are long-lasting and interfere with the pregnant woman's/mother's daily routine, researchers may file the effect(s) as an adverse event. Side effects that meet a criterion for an SAE should be reported with the reason noted.

In addition to serious adverse events (SAEs), adverse events will be captured and reported on a regular basis. Such events will include those noted as secondary outcomes, exclusive of those conditions that, by definition, must be reported as an SAE or an unexpected drug reaction by the regulatory authorities. The DSMB may additionally request information on other events it believes may pose relevant risk.

Specific forms will be utilized to report an SAE or an AE. For an SAE, the reporting form should be sent to the person designated to receive it within 7 days of the notification of the event to the study team. Reportable adverse and serious adverse events will be shared with the Data and Safety Monitoring Board as will the determination made by two independent adjudicators (with expertise in iron infusion) about whether the SAE is associated or not with the IDA treatment approaches used in this study. Adjudicator reports will also be provided to the Principal Investigator, Senior Foreign Investigator and the Chief Quality and Safety Officer.

If there is an unanticipated problem recognized as posing a risk to participants or others and it is likely to reoccur within one or multipe research sites, a designated researcher associated with the site should obtain additional information on the unanticipated event and compile a report to forward to the study Principal Investigator, Chief Quality and Safety Officer and the Chair of the DSMB. The Chair will review the report and determine significance of the event to the study and the need for action to avoid harm to participants. The Chair may put the report on the agenda of the next DSMB meeting or communicate with members to address the unanticipated problem sooner.

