- Hb 7 9.9 g/dL, TSAT <20% and/or ferritin < 30 ng/mL as determined by the analysis of blood drawn at visit #1

Randomize an eligible woman; inform participant of randomization to the oral iron arm or an IV iron infusion arm (but not which one) Collect socioeconomic status data, dietary information, height and weight, blood pressure, other data specific to this visit for a woman determined eligible for continued study participation and randomization, and complete study data form

- A participant randomized to the oral iron arm receives deworming medication, tablets that will provide the recommended daily doses of iron and folic acid along with instructions consistent with Ministry of Health and Family Welfare (MOHFW) guidelines
- A participant randomized to an IV iron arm receives deworming medication and folic acid consistent with the daily dosage guideline; the IV iron infusion is arranged at a CHC—on the same day (or, based upon case-by-case consideration, on a day not later in the pregnancy than 17 weeks 0 days)

Progression of RAPIDIRON Trial Participants through Milestones and Visits, continued

Week of Pregnancy (P)

14P 15P 16P 17P 18P 19P 20P 21P 22P 23P 24P 25P 26P 27P 28P 29P 30P 31P 32P 33P 34P.....

Visit #3a: At a CHC for an IV iron arm pregnant woman, between 14 weeks and 17 weeks 0 days of pregnancy

Counsel the pregnant woman about the infusion procedure, risks and benefits and confirm willingness to receive the infusion Provide the IV iron infusion using the correct formulation prepared by the CHC pharmacist (using randomization number and body weight) Monitor the participant for the recommended time after infusion

Complete the study data form, including information relevant to the infusion

Visit #4: At an IV iron arm participant's PHC or CHC, 2 weeks post receipt of an IV iron infusion

Draw a blood sample from an IV iron arm participant and send it to the designated central laboratory for analysis of serum phosphate level (See Note 1)

Visit #5: At participant's PHC or CHC, 20-24 weeks of pregnancy

Monitor the participant's pregnancy per guidelines

Draw blood samples to determine Hb, TSAT, and ferritin (**See Note 1**)

Collect data specific for this visit (participant weight, blood pressure, etc.), complete study data form Send blood samples to the central laboratory for analysis and distribution of results

Visit #6: At participant's PHC or CHC, 26-30 weeks

Monitor the participant's pregnancy per guidelines

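### Fetal losses between treatment (14 weeks to 17 weeks 0 days) and 20 weeks are not automatically SAEs, so how they are classified depends on admission practice and unmasked judgement

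*Combined protocol and SAP*

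**What the plan says.** **Definition.** Under H.2 an SAE "involves a randomized participant that initiated treatment OR the fetus or newborn of such a participant", and one criterion is enough: "To qualify as an SAE, at least one criterion below will apply to the event". The death criterion is "Results in a maternal or neonatal death, or a fetal death greater than 20 weeks gestation". The other criteria have no gestational limit. They are a threat to life, disability, any other serious or unexpected event that the investigator thinks should be reported, and this one: "Requires an unanticipated hospitalization or prolongs an existing hospitalization".

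**Timing.** Appendix B places the infusion visit (#3a) as follows: "At a CHC for an IV iron arm pregnant woman, between 14 weeks and 17 weeks 0 days of pregnancy". Oral participants are randomized in the same gestational window.

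**What SAE status brings.** H.2 sets a 7-day limit for the SAE form and has two adjudicators judge whether the SAE is related to treatment. Section J says they validate every SAE case by case. H.1 describes email review between DSMB meetings for an SAE; scheduled meetings are about six months apart. In E.4 the DSMB considers stopping enrollment to an IV arm if the intervals show "significantly higher risk of either mortality or adjudicated SAE incidence than the active comparator arm".

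**What happens to other events.** Pregnancy loss is a secondary outcome in E.3.B, listed apart from stillbirth. H.2 says of the adverse events captured and reported regularly: "Such events will include those noted as secondary outcomes, exclusive of those conditions that, by definition, must be reported as an SAE".

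**Infants.** Participation ends about 42 days after delivery (Section F), and E.5 promises descriptive statistics on infant mortality. The H.2 death criterion stops at the neonatal period.

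**The concern.** The weeks just after treatment are when an effect of the infusion on the pregnancy would be looked for first. In that period the plan has no rule that makes a fetal loss an SAE. The loss becomes one only if the woman is admitted, her life is threatened, or someone decides to escalate it.

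That is a weak basis for comparing arms. Section D leaves oral iron unmasked, so staff who decide whether to escalate a loss know whether the woman had an infusion. Contact differs too: visit #4 is for IV participants only. Differential classification could bias the SAE comparison in either direction. It could hide an excess in the IV arms, or create one if losses after an infusion are escalated more readily.

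The same SAE count feeds the E.4 harm rule. E.4 also does not say whether its mortality component covers fetal or infant deaths, so that component cannot be relied on to pick up what the SAE definition leaves out.

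**Working it through.** The plan states no figure for early loss, so there is none to reproduce. The check sets the sections side by side and bounds the number of events.

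**1. Length of the window.** The threshold is 20 weeks (H.2) and treatment is at 14 weeks to 17 weeks 0 days (Appendix B).
- Treated at 17 weeks 0 days: 20 − 17 = 3 weeks.
- Treated at 14 weeks: 20 − 14 = 6 weeks.

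**2. Contact inside the window.** Visit #4 is two weeks after the infusion, so at 14 + 2 = 16 weeks to 17 + 2 = 19 weeks. That falls before the threshold for every IV participant. The next scheduled study visit for an oral participant is #5, at 20 to 24 weeks. A loss therefore has one scheduled occasion to be noted in the window in the IV arms and none in the oral arm.

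**3. Route of a loss at or before 20 weeks.**

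| Circumstance | Class under H.2 | 7-day form | SAE adjudication | SAE part of E.4 rule |
|---|---|---|---|---|
| Life-threatening | SAE | Yes | Yes | Yes |
| Unanticipated or prolonged hospitalization | SAE | Yes | Yes | Yes |
| Investigator chooses to report it | SAE | Yes | Yes | Yes |
| None of these | AE, through the secondary outcome | No | No | No |

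A loss after 20 weeks gets all three automatically.

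**4. Number of losses affected.** E.1 gives about 4,320 women randomized 1:1:1, and 4,320 / 3 = 1,440 per arm. Let r be the risk of loss between treatment and 20 weeks, and f the share of those losses that qualify as SAEs by another criterion. The number not counted as SAEs is 1,440 × r × (1 − f) per arm. Both r and f are assumptions.

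| r (assumed) | f = 0 (upper bound) | f = 0.5 |
|---|---|---|
| 0.5% | 1,440 × 0.005 = 7.2 | 3.6 |
| 1.0% | 1,440 × 0.010 = 14.4 | 7.2 |
| 1.5% | 1,440 × 0.015 = 21.6 | 10.8 |

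Across three arms the upper bound is 3 × 7.2 = 21.6 to 3 × 21.6 = 64.8, or about 22 to 65 events.

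**5. Infant deaths.** The documents do not define neonatal. If it means the first 28 days (an assumption), follow-up to day 42 leaves 42 − 28 = 14 days in which a death does not meet the death criterion.

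**The case against.** The strongest reply is that these losses are not lost to safety oversight, and that is correct. A reader might infer that every loss before 20 weeks escapes reporting, adjudication and the harm rule. The documents do not support this:

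- The other SAE criteria have no gestational limit, and SAEs explicitly include events in the fetus.
- Remaining losses are captured as adverse events, and H.2 sends adverse events as well as SAEs to the DSMB.
- The DSMB may expand the reporting list (H.1), ask for other events (H.2) and weigh the overall risk profile (E.4).
- H.2 has a route for unanticipated problems that goes straight to the DSMB Chair.
- The Abstract has adjudicators assess adverse reactions to oral or IV iron, so their work is not confined to SAEs.
- E.4 leaves mortality undefined, so it neither includes nor excludes fetal death.

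A 20-week cut-off with adverse-event capture below it can also be defended as a design choice.

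What remains is narrower. The reaction and unanticipated-problem routes require someone first to suspect a drug reaction or recognise a risk, whereas adjudication exists to decide whether an event is related. DSMB discretion does not make the classification uniform across arms. The investigator criterion is itself a judgement made with knowledge of IV versus oral assignment.

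**Conclusion.** The point holds in limited form, with high confidence as to the text. No rule makes a fetal loss in the 3 to 6 weeks after treatment an SAE. Its 7-day form, SAE adjudication and count in the SAE part of the harm rule therefore depend on admission practice, severity or unmasked judgement. The infant gap is smaller; it depends on how neonatal and newborn are read, and the hospitalization and discretionary criteria may close part of it.

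The size is at most about 7 to 22 losses per arm, under an assumed risk of 0.5 to 1.5%. It is an upper bound for two reasons: some losses would qualify by another criterion, and women treated at 17 weeks 0 days have half the window of those treated at 14 weeks.

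A reader might also infer that rewording would let the E.4 rule detect an early-loss signal. That does not follow. With an assumed doubling from 1% to 2%, a two-sided test at 0.025 on early losses alone has about 23% power with 666 per arm (the futility snapshot, used here as an illustrative size) and about 49% with 1,440. Within the SAE total, these losses would be further diluted by other events. The gain is consistent classification and adjudication of events close to exposure. This should be corrected, but it does not touch the primary analyses.

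**What to change.** 1. In H.2, replace the death criterion with: *maternal death; any fetal death or pregnancy loss, at any gestation, after treatment initiation; or infant death through visit #9*. Starting at treatment initiation matches the SAE population that H.2 already defines.
2. In E.4, state whether mortality includes fetal and infant death, and align E.5 and the Interim Analysis Plan with that.
3. Tabulate losses up to 20 weeks and after 20 weeks separately by arm, so that figures at the existing threshold stay available.

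The cost is wording in the protocol and on the SAE form, plus a few dozen more SAE forms and adjudications across the trial (at most about 22 to 65 at the assumed rates) for the adjudicators already appointed. Pregnancy loss is already collected as a secondary outcome. The change removes the judgement step in classifying a loss. It does not remove the difference in scheduled contact between the IV and oral arms, which should be borne in mind when the table is read.
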